### **8.3.2     *Definition of Serious Adverse Events (SAE)***

A serious adverse event (SAE) is defined by federal regulation as any AE occurring at any dose that results in any of the following outcomes: death, life-threatening AE, requires hospitalization or prolongation of existing hospitalization, a persistent or significant disability/incapacity, or a congenital anomaly/birth defect. All SAEs will be documented during trial.

Important medical events that may not result in death, be life threatening, or require hospitalization may be considered an SAE when, based upon appropriate medical judgment, they may jeopardize the subject and may require medical or surgical intervention to prevent one of the outcomes listed in this definition. Examples of such medical events include allergic bronchospasm requiring intensive treatment in an emergency room or at home, blood dyscrasias or convulsions that do not result in subject hospitalization, or the development of drug dependency or drug abuse.

### **8.3.3     *Unanticipated Adverse Device Effect (UADE)***

#### Risk of Misinterpretation

Errors may occur with the use of OTL38 during intraoperative fluorescence imaging to detect ovarian cancer and lesions in the lung, including false negatives and false positives. Non-fluorescing tissue in the surgical field does not rule out the presence of ovarian cancer or lesions in the lung. Fluorescence may be seen in normal tissues including bowel, kidneys, lymph nodes, and lungs as well as in inflamed tissues.

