### **5.1     Inclusion Criteria**

In order to be eligible to participate in this study, an individual must meet all of the following criteria:

1. Provision of signed and dated informed consent form
2. Adult subjects 18 years of age and older
3. Primary diagnosis of endometrial cancer
4. Scheduled to undergo surgery for endometrial cancer
5. Ability to understand the requirements of the study and agree to abide by the study restrictions and to return for the required assessments

03 Sep 2025

6. Willingness to stop the use of folate or folic acid supplements at least 48 hours prior to infusion of study drug

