### **6.3 Measures to Minimize Bias – Randomization and Blinding**

This trial will be an open-label study with no randomization or blinding. All subjects will receive the study drug.

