#### 8.1.3 Visit 2: Surgery

*[Purpose: To collect data on the performance of intra-operative molecular imaging]*

1. AEs and ADEs will be recorded during and following surgery.

03 Sep 2025

2. After the surgical site is visualized under normal light and/or palpation, the number and location of suspect lesions detected under normal light will be recorded on the schematic using an “O”.
3. Following the assessment by normal light, subjects will undergo fluorescence imaging of the surgical field. Suspect lesions detected under fluorescence imaging will be marked on the schematic using an “X”.
4. All identified suspect lesions will be marked on the schematic (“O”, “X”, or “⊗” as described in [Section 4.1.3](#)) and excised, at the discretion of the Investigator.
5. Sentinel lymph node biopsy will be performed at the Investigator’s discretion per the standard of care.
6. All excised lesions will be sent to the local laboratory for histopathology and immunohistochemistry staining. A unique identifier will be assigned to each excised lesion and the location of each will be recorded along with the unique identifier. If an organ/large section of tissue (e.g. uterus, omentum) with multiple lesions is excised *in toto*, one grossly positive lesion will be utilized for the purposes of calculating sensitivity and FR expression.
7. Histopathology, folate receptor expression, and genomic testing results will be recorded once data is received per institutional practices and timeline.

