## 9 STATISTICAL CONSIDERATIONS

### 9.1 Statistical Hypotheses

- Primary Efficacy Endpoint:
  - The primary efficacy endpoint is the sensitivity of CYTALUX with NIR imaging for detection of malignant lesions. Sensitivity is defined as the proportion of fluorescent light positive lesions that are histologically confirmed to be cancer relative to the total number of lesions confirmed to be cancer.  
Sensitivity = (True Positive)/(True Positive + False Negative)
- Secondary Efficacy Endpoints:
  1. Incidence rates of all adverse events (AEs), adverse device effects(ADEs), and SAEs, from the time of CYTALUX administration through Visit 3
  2. Sensitivity for cancerous lesions for:
    - a. FR $\alpha$  positive lesions
    - b. FR $\beta$  positive lesions
- Exploratory Endpoints:
  1. Genomic evaluation of tumor inclusive of, but not limited to:
    - a. Estrogen receptor/progesterone receptor (ER/PR) status
    - b. HER2 status
    - c. Mismatch repair (MMR) status
    - d. POLE status
    - e. p53 status
    - f. CARIS whole genome sequencing
  2. The exploratory endpoint is the detection rate of CYTALUX with NIR imaging for identification of SLNs. The detection rate is the proportion of the patients with SLNs detected by CYTALUX and NIR imaging in all enrolled patients.

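### Normal-light suspects are excised at discretion after the unblinded NIR result is known, so a non-fluorescing cancer left in place cannot count as a false negative and the primary sensitivity may be biased upward

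*Protocol*

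**What the plan says.** **Order of steps (Protocol 8.1.3).** Step 2 has the surgeon record the number and location of suspects seen under normal light, marked O. Step 3 follows: "Following the assessment by normal light, subjects will undergo fluorescence imaging of the surgical field", with fluorescing suspects marked X. In step 4 all suspects, whether O, X or both, are marked "and excised, at the discretion of the Investigator". Section 6.3 states: "This trial will be an open-label study with no randomization or blinding". The fluorescence result is therefore known when the excision decision is taken.

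**Reference standard (8.1.3, step 6).** "All excised lesions will be sent to the local laboratory for histopathology and immunohistochemistry staining". No histology is provided for a lesion that is not excised.

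**Endpoint (1.1, 3 and 9.1).** Sensitivity is TP/(TP + FN), taken "relative to the total number of lesions confirmed to be cancer".

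**Analysis (9.2.2).** Subjects who were dosed and imaged are included. The proportion is tested against 0.10 by an exact binomial test at two-sided 0.05, with a 95% confidence interval. The section does not say how marked but unexcised lesions are handled.

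**Counterweight (1.1 and 4.1.3).** Tissue removed as standard of care is imaged before and after resection and compared with pathology, whether or not it fluoresces.

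**Misinterpretation text (8.3.3).** "Non-fluorescing tissue in the surgical field does not rule out the presence of ovarian cancer or lesions in the lung". The inclusion criterion in 5.1 is "Primary diagnosis of endometrial cancer".

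**The concern.** In a diagnostic accuracy study, the choice of lesions that get the reference standard should not depend on the index test. Here it can. The surgeon sees the fluorescence result first and then decides what is removed, and only removed tissue can become a confirmed cancer.

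The lesions at issue are those marked O only: suspect under normal light, dark under NIR. If such a lesion is cancer and is excised, it is a false negative. If it is cancer and is left, it drops out of the denominator while the numerator stays the same. This is partial verification, and it bears on the primary estimate and its interval.

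The protocol does not fix the excision plan before NIR. What the surgeon intended at that moment cannot be reconstructed at analysis if it was not written down in theatre.

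**Working it through.** **Inputs from the Protocol.** Null value 0.10, two-sided alpha 0.05, exact binomial test (9.2.2); 10 subjects (1.1). No expected sensitivity, power or lesion count is stated, so there is no planned figure to reproduce.

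**Assumed inputs.** 20 malignant lesions, treated as independent; true sensitivity S; fraction u of dark cancers left in place; fraction v of fluorescing cancers left in place.

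**1. Direction.** Expected observed sensitivity is approximately

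S(1 − v) / [S(1 − v) + (1 − S)(1 − u)].

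- If u = v, the factors cancel and there is no bias.
- If u > v, the bias is upward.
- If u < v, it is downward.

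The concern needs dark suspects to be left more often than fluorescing ones.

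**2. Size with v = 0.** The formula becomes S / [S + (1 − S)(1 − u)].

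| True S | u = 0.25 | u = 0.50 | u = 0.75 |
|---|---|---|---|
| 0.50 | 0.571 | 0.667 | 0.800 |
| 0.60 | 0.667 | 0.750 | 0.857 |
| 0.80 | 0.842 | 0.889 | 0.941 |

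**3. In counts.** Take 20 cancers, 12 fluorescing and 8 dark.

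| Dark cancers left | Observed | Exact 95% CI |
|---|---|---|
| 0 | 12/20 = 60.0% | 36.1 to 80.9% |
| 2 | 12/18 = 66.7% | 41.0 to 86.7% |
| 4 | 12/16 = 75.0% | 47.6 to 92.7% |

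**4. Effect on the test at moderate sensitivity.** For 12/20 the exact p against 0.10 is already below 0.000001. Leaving dark cancers cannot change that conclusion.

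**5. Effect on the test at low sensitivity.** Take 20 cancers, of which 4 fluoresce. Two conventions for the two-sided exact p are shown: minimum likelihood (sum of all outcomes no more probable than the one observed) and the doubled upper tail.

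| Dark cancers left (of 16) | Observed | p, minimum likelihood | p, doubled tail | Exact 95% CI |
|---|---|---|---|---|
| 0 | 4/20 = 20.0% | 0.133 | 2 × 0.133 = 0.266 | 5.7 to 43.7% |
| 6 | 4/14 = 28.6% | 0.044 | 0.088 | 8.4 to 58.1% |
| 8 | 4/12 = 33.3% | 0.026 | 0.051 | 9.9 to 65.1% |

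The result crosses 0.05 under the first convention only. Both shifted intervals still include 0.10. The true value in this example is 20%, above the threshold, so the crossing is not itself a false-positive claim.

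**6. False-positive rate at S = 0.10.** With TP ~ Bin(20, 0.10), verified FN ~ Bin(20 − TP, 1 − u) and v = 0, full enumeration under the minimum-likelihood convention gives a chance of declaring efficacy of 0.043, 0.060, 0.137 and 0.290 for u = 0, 0.25, 0.50 and 0.75. So the error rate can be inflated, but only if true sensitivity is near 0.10 and a large share of visible dark cancers is left.

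**The case against.** **Standard-of-care tissue is verified regardless.** This stands as a limit on size. Subjects are scheduled for endometrial cancer surgery, and under 8.1.3 step 6 an organ or large section with multiple lesions removed whole contributes one grossly positive lesion. With 10 subjects, such specimens may be a substantial share of the lesions counted, and little of this bias reaches them. It does not cover a marked suspect that is not removed.

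**Nothing shows that dark suspects will be left.** This also stands. The Protocol does not tell the surgeon to spare non-fluorescing tissue. Section 2.3 describes NIR as used together with palpation and visual observation, and 2.4.2 lists no tissue-sparing benefit. A reader might infer that false negatives are likely to be left in place; the document does not support that.

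**The threshold of 0.10 is easily cleared.** Largely true. A reader might infer that the efficacy conclusion is at risk. That needs a true sensitivity around 0.10 to 0.20 and many visible cancers left, 6 to 8 of 16 in the example. Even then it turns on the two-sided convention.

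**The 8.3.3 wording causes the problem.** A reader might link the two, but that text governs neither excision nor the denominator. Adding endometrial cancer to it would leave the estimate unchanged.

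**Much of this could be derived or left to the SAP.** In part. Step 2 records O lesions, step 6 gives each excised lesion an identifier, and 4.1.4 keeps a specimen inventory, so unexcised O-only lesions can largely be counted by subtraction. A supplementary analysis is ordinary SAP content. The intention before NIR is different: it has to be captured at surgery.

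**Conclusion.** The concern holds in a limited form. As written, verification can depend on the index test, and an O-only cancer left in place cannot enter TP + FN. If dark suspects are left more often than fluorescing ones, sensitivity and its confidence interval are biased upward. The size is unknown. On the assumed 12 of 20, leaving 2 to 4 of the 8 dark cancers moves the estimate from 60% to 67 to 75%.

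The harm is mainly to the estimate and interval. The test decision is exposed only at low true sensitivity. These figures rest on an assumed lesion count, independence of lesions and removal of all fluorescing cancers. The change is worth making because it is cheap and the information cannot be recovered afterwards. The 8.3.3 wording is a separate editorial correction.

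**What to change.** 1. **Surgical schematic and 8.1.3.** For each O lesion, record before NIR is switched on whether excision is planned (yes/no).
2. **Section 9.2.2, reporting.** Report the number of marked lesions not excised, by NIR status (O only, X only, both), with the reason. The split shows whether dark suspects were in fact left more often.
3. **Section 9.2.2, supplementary analysis.** Add a lower-bound sensitivity with its 95% CI that counts O-only lesions planned for excision but left as false negatives. State that it is conservative, since some may be benign or left for other reasons. For example, with 12/16 observed and 4 such lesions it is 12/(16 + 4) = 60%; if 2 further benign ones were also left, it would be 12/(16 + 6) = 54.5%.
4. **Wording only.** Reconcile the 8.3.3 misinterpretation text, which names ovarian and lung disease, with the endometrial population.

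The cost is one entry per normal-light lesion, a short table and a less favourable bound beside the primary estimate. If no planned O-only lesion is left, the bound equals the primary estimate and supports it. Surgical decisions are unaffected.

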### **8.3.4     *Classification of an Adverse Event (AE)***

#### **8.3.4.1     *Severity of Event***

The severity of all AE will be assessed by the Investigator and should be classified as mild, moderate, or severe. Severity will be graded according to the following definitions:

**Mild:** The subject experiences awareness of symptoms but these are easily tolerated or managed without specific treatment. Clinical or diagnostic observations only, intervention is not indicated.

03 Sep 2025

**Moderate:** The subject experiences discomfort enough to cause interference with usual activity, and/or the condition requires specific treatment. Minimal, local or non-invasive intervention is indicated.

**Severe:** The subject is incapacitated with inability to work or do usual activity, and/or the event requires significant treatment measures. Not immediately life-threatening but requires or prolongs hospitalization.

**Life Threatening:** Urgent intervention is indicated.

**Fatal:** The adverse event results in death or is death.

#### **8.3.4.2      *Relationship to Study Intervention***

AEs must have their relationship to study intervention assessed by the clinician who examines and evaluates the participant based on temporal relationship and his/her clinical judgment. The degree of certainty about causality will be graded using the categories below. In a clinical trial, the study product must always be suspect.

- **Related** – There is evidence to suggest a causal relationship, and the influence of other factors is unlikely. The clinical event, including an abnormal laboratory test result, occurs within a reasonable time after administration of the study intervention, is unlikely to be attributed to concurrent disease or other drugs or chemicals, and follows a clinically reasonable response on withdrawal (dechallenge). Rechallenge information is not required to fulfill this definition.
- **Not Related** – A clinical event, including an abnormal laboratory test result, whose temporal relationship to study intervention administration makes a causal relationship improbable (e.g., the event did not occur within a reasonable time after administration of the study intervention) and in which other drugs or chemicals or underlying disease provides plausible explanations (e.g., the participant's clinical condition, other concomitant treatments). Or, the AE is completely independent of study intervention administration, and/or evidence exists that the event is definitely related to another etiology. There must be an alternative, definitive etiology documented by the clinician

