#### **8.3.4.3      *Expectedness***

The Investigator will be responsible for indicating whether an adverse event (AE) is expected or unexpected. An AE will be considered unexpected if the nature, severity, or frequency of the event is not consistent with the patient population under study, the known risks of major surgery, or the risk information previously described for the study intervention.

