### **9.2.3 Safety Analyses**

Safety will be described via subject incidence of treatment emergent adverse events (TEAEs) including serious TEAEs as well as adverse device effects (ADEs) considered as causally related.

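### The only causality scale (8.3.4.2) is written for a drug reaction, and with the 8.3.1 documentation filter it can leave non-serious harm from fluorescence-led excision or the camera out of the safety data

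*Protocol*

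**What the plan says.** Section 8.3.4.2 states that "AEs must have their relationship to study intervention assessed by the clinician who examines and evaluates the participant", using temporal relationship and clinical judgment. There are two grades. 'Related' begins with "There is evidence to suggest a causal relationship, and the influence of other factors is unlikely", adds that the event "occurs within a reasonable time after administration of the study intervention, is unlikely to be attributed to concurrent disease or other drugs or chemicals", and ends with the condition that it "follows a clinically reasonable response on withdrawal (dechallenge". 'Not Related' requires a documented alternative, definitive cause.

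Other sections bear on what this scale must cover:

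- Section 8.3.1 defines an ADE as an AE linked to a medical device and names the camera and NIR light as examples. It tells the investigator to consider AEs against trial procedures as well as the product. It also says that only AEs and ADEs judged to be caused by the investigational product are documented.
- Section 8.3.3 warns of false positives: "Fluorescence may be seen in normal tissues including bowel, kidneys, lymph nodes, and lungs as well as in inflamed tissues".
- Section 8.1.3 has suspect lesions marked O, X or ⊗ "and excised, at the discretion of the Investigator". X alone means seen only under fluorescence.
- Section 2.4.1 names sterile-field contamination and injury from a disengaged camera part as risks.
- Sections 1.1, 3 and 9.1 set the secondary safety endpoint as the incidence of all AEs, ADEs and SAEs from administration to Visit 3.
- Section 9.2.3 reports treatment-emergent AEs, serious ones, and "adverse device effects (ADEs) considered as causally related".

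**The concern.** An imaging agent can cause harm in three ways: through the drug, through the device, and through what the surgeon removes because of the image. The protocol recognises all three in sections 2.4.1, 8.3.1 and 8.3.3, but its grading rule is built for the first. The grade matters because section 8.3.1 makes it the condition for documenting a non-serious event. If harm led by imaging does not fit 'Related', it can leave the data before analysis, and the safety summary for secondary objective 1 could then show fewer imaging-related events than occurred.

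**Working it through.** The protocol states no figure on this point, so the check is to take two events it foresees and run each through its own rules.

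Event A: a non-serious injury at a site where tissue marked X only was removed and proved benign. Event B: a non-serious injury from a disengaged camera part.

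| Element of 'Related' (8.3.4.2) | Event A | Event B |
|---|---|---|
| Other factors unlikely | Surgery is an obvious other factor | The camera is itself another factor if the intervention is read as the drug |
| Reasonable time after administration | May be met, but says little: imaging starts 1 to 168 hours after the infusion ends, and the injury is timed by the excision | Same; the injury is timed by camera use |
| Not due to disease, other drugs or chemicals | Met, but does not address excision | Met, but does not address the device |
| Dechallenge | No meaning for an excision injury after a completed single infusion | No meaning for a mechanical injury |

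Next, 'Not Related'. One route is that the event is independent of administration or has another definite cause, which the clinician documents. Surgical dissection (A) or the camera (B) can be written down as that cause. The wording therefore leans towards 'Not Related' for both events.

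Then follow the grade forward.

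1. Documentation. Section 8.3.1 defines an AE by reference to a medicinal product, names the device separately, and sets product and procedures side by side. 'Investigational product' in its documentation sentence therefore reads most naturally as the drug. On that reading, A and B, graded 'Not Related' and non-serious, are not documented.
2. Endpoint. Sections 1.1, 3 and 9.1 promise all AEs and ADEs. The documentation sentence in 8.3.1 contradicts this.
3. Analysis. Section 9.2.3 needs a causality judgment on ADEs, but 8.3.4.2 supplies no device criterion for making one.
4. If A or B is serious, section 8.3.2 documents it and 8.3.6 requires notice to the principal investigator whatever the attribution. The event is kept, but no grade ties it to imaging.
5. Grades. Section 8.3.6 refers to definite, probable or possible relationship. Section 8.3.4.2 has only two grades, so the reporting rule uses categories the scale does not produce.

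Size. With 10 planned subjects, one affected subject is 1/10 = 10 percentage points. If the event is left out, the reported incidence is 0/10 instead of 1/10. This is the weight of a single event and does not estimate how often one occurs.

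**The case against.** The strongest reply is that the protocol already covers much of this ground. Camera and NIR harm is defined as an ADE, scheduled at Visits 2 and 3, recorded during surgery, included in a secondary endpoint and analysed. Section 6, on the study intervention, includes the imaging system at 6.1.3, so the intervention need not mean the drug alone. Section 8.3.1 tells investigators to consider procedures. The scale allows clinical judgment, holds the product always suspect, and asks for a definitive alternative cause before 'Not Related'. SAEs are documented and go to the IRB under its policies. A count of benign X-only excisions could be left to an analysis plan.

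Most of this stands, and it rules out several stronger readings that a reader might infer.

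- That such harm can never be graded 'Related'. Clinical judgment leaves room; the definition fits badly but does not forbid the grade.
- That it goes unmeasured. Serious events are kept, and X marks, locations and histology are recorded.
- That it is hidden by the expectedness rule in 8.3.4.3. An event is unexpected when it is "not consistent with the patient population under study, the known risks of major surgery", or out of line with the intervention's risk information. That is a separate question from causality, and an expected event can still be related.
- That this is the main risk of the agent. The protocol does not rank it so.
- That the 25% to 40% in section 2.3 gives its frequency. That figure, from ovarian and lung studies, counts additional cancer or positive margins found, not benign tissue removed or complications.

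The reply does not answer two things: the instruction to consider procedures has no grade in 8.3.4.2 to record the result, and the documentation sentence in 8.3.1 is tied to the product.

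**Conclusion.** The point holds as a defect in the attribution and documentation rules. The 'Related' definition suits a drug reaction, fits fluorescence-led excision poorly and has no device criterion. Together with the filter in 8.3.1, it allows non-serious imaging-led harm to be left out of an endpoint defined on all AEs and ADEs. Serious harm is kept without attribution to imaging.

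The frequency cannot be derived: the protocol gives no rate of benign X-only excision or of complications from it. The conclusion rests on two assumptions: that investigators apply 8.3.1 and 8.3.4.2 as worded, and that 'investigational product' means the drug. The AE form is not shown and might soften the effect, but the protocol text would still contradict itself. The change is worth making because it is cheap and secondary objective 1 is safety.

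**What to change.** - **8.3.4.2:** grade relationship separately to (a) CYTALUX, (b) the NIR imaging system, and (c) excision or added dissection prompted by fluorescence alone, marked X and not ⊗. Apply time since administration and dechallenge only to (a).
- **8.3.1:** align the documentation sentence with the endpoint of all AEs and ADEs, or at least extend it to all three attributions.
- **8.3.6:** reconcile its definite, probable or possible wording with the two grades in 8.3.4.2.
- **9.2.3:** report AEs by attribution, with the number of X-only excisions that had benign histology.

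The cost is two extra fields on the AE form and one table. The marks, specimen locations and histology are already collected under 4.1.3, 8.1.3 and 8.2.2. The small downside is that some surgical complications will be reported as imaging-related.
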